### 13.5 Secondary Endpoints

The following are secondary endpoints for this study:

- Change from Baseline in:
  - IDUA activity measured in blood.
  - Total GAG, DS GAG, and HS GAG levels (expressed as ratio to creatinine) measured in urine.
  - Monthly and annualized frequency and dose of Aldurazyme (or equivalent ERT).
- AAV2/6 clearance measured by vector genomes in plasma, saliva, urine, stool, and semen by PCR.

At each sampling time point, the actual value and the change from baseline for IDUA activity and GAG levels in urine will be summarized using descriptive statistics and plotted over time by treatment cohort.

For subjects who undergo ERT withdrawal, changes from pre- to post- ERT withdrawal in the frequency and dose of ERT infusions will be evaluated and summarized using monthly, quarterly, and annualized total dose and number of infusions. Duration of ERT withdrawal may also be analyzed.

AAV2/6 clearance measured by vector genomes in the different samples will be plotted over time by treatment cohort.

### 13.6 Exploratory Endpoints

The following are exploratory endpoints for this study:

- Change from Baseline in:
  - Total GAG, DS GAG, and HS GAG levels measured in tissues (including blood, liver tissue, and CSF).
  - Percentage and durability of gene modification at the albumin locus in liver tissue obtained at biopsy.
  - Forced vital capacity measured by PFTs.
  - Distance walked measured by 6MWT.
  - JROM.
  - MRI of liver to evaluate liver and spleen volume.
  - MRI of brain and cervical spine to evaluate clinical soft tissue and/or bone.
  - Neurocognitive abilities by WASI-II, WPPSI-IV, or BSID-III, and by VABS-II.
  - Eye exam for corneal clouding and vision testing.
  - Histopathological exam of liver tissue.
  - Immune response to AAV 2/6, ZFNs, and IDUA measured in serum.

Analysis details for the exploratory endpoints will be provided in the Statistical Analysis Plan.

## **14 INVESTIGATOR OBLIGATIONS**

The Principal Investigator will ensure that the study is conducted in compliance with the protocol, Declaration of Helsinki, ICH Guidelines for Good Clinical Practice (E6), and all regulatory and institutional requirements, including those for subject privacy, informed consent, IRB/IEC or equivalent approval, and record retention.

### **14.1 Informed Consent**

No investigator may involve a human being as a subject in research covered by these regulations unless the investigator has obtained the legally effective informed consent of the subject or the subject's legally authorized representative. An investigator shall seek such consent only under circumstances that provide the prospective subject sufficient opportunity to consider whether or not to participate, and that minimize the possibility of coercion or undue influence. The information that is given to the subject or the representative shall be in language understandable to the subject or the representative.

Sangamo will provide the Principal Investigator with a template for the consent form. State and local laws and/or institutional requirements may require the disclosure of additional information in the informed consent. The proposed consent form must be submitted to Sangamo prior to submission to the IRB/IEC or equivalent to ensure that it meets Sangamo standards for consent forms. The IRB/IEC or equivalent must approve the consent form. A copy of the approved form must be submitted to Sangamo.

Prior to the initiation of any procedures relating to the study, informed consent shall be documented by the use of a written consent form approved by the IRB/IEC or equivalent and signed and dated by the subject at the time of consent. A copy of the signed informed consent will be given to the person signing the form. The Principal Investigator must keep each subject's signed consent form on file for inspection by a regulatory authority at any time.

### **14.2 Institutional Review Board/Ethics Committee and BioSafety Committee**

This protocol, informed consent document, and relevant substantive data are to be submitted to the appropriate IRB/IEC or equivalent and BioSafety Committee (BSC) for review and approval before the initiation of the study. Amendments to the protocol will also be submitted to the IRB/IEC or equivalent and BSC (as appropriate) prior to implementation of the change. A letter documenting the IRB/IEC or equivalent and BSC approval must be received by Sangamo prior to initiation of the study.

### **14.3 Protocol Amendments**

Any changes to this protocol will be initiated by Sangamo in writing as a protocol amendment. The amendment must be submitted to the IRB/IEC or equivalent together with a revised informed consent form, if applicable. Written documentation of IRB/IEC or equivalent approval must be received before the amendment may take effect.

### **14.4 Subject Privacy**

Subject medical information obtained for the purposes of this trial is confidential, and disclosure to third parties other than those noted below is prohibited. Upon the subject's request and written permission, medical information may be given to the subject's personal physician or other appropriate medical personnel responsible for the subject's welfare. Data generated for this study must be available for inspection on request to representatives of the appropriate regulatory

authorities (e.g., FDA/MHRA or equivalent), other national or local health authorities, Sangamo, and the associated IRB/IEC or equivalent.

Release of research results or data that reveal subject names or other identifiers, such as photographs, audio, or videotapes, must be carried out in accordance with Department of Health and Human Services Standards for Privacy of Individual Health information, 45 CFR 164.508. Written authorization must be obtained from the subject and IRB/IEC or equivalent prior to release of such information. Identifiable subject data may not be used for purposes of promoting the investigational product.

#### **14.5 Reporting Obligations**

Sangamo, the Sponsor of this study, is required to report to the regulatory authorities (e.g., FDA/MHRA or equivalent) annually on the status of the trial. Status reports must be filed by the Principal Investigator with his/her IRB/IEC or equivalent on an annual basis.

The Principal Investigator is also responsible for informing his/her IRB/IEC or equivalent of the progress of the study and for obtaining annual IRB/IEC or equivalent renewal. The IRB/IEC or equivalent must be informed at the time of completion of the study. The Principal Investigator should provide his/her IRB/IEC or equivalent (if required by the institution) with a summary of the results of the study.

## **15 ADMINISTRATIVE CONSIDERATIONS**

### **15.1 Study Documentation**

The Principal Investigator and study staff are responsible for maintaining a comprehensive and centralized filing system containing all study-related documentation. These files must be suitable for inspection by Sangamo or regulatory authorities (e.g., FDA/MHRA or equivalent) at any time, and should consist of the following elements:

- Subject files containing the completed medical records, supporting source documentation, electronic CRFs, and the IRB/IEC or equivalent approved Informed Consent signed by subjects.
- Study files containing all versions of the IRB/IEC or equivalent approved protocol with all amendments, IRB/IEC or equivalent approved informed consent forms, copies of all pre-study documentation, Form FDA 1572, and all correspondence to and from the IRB/IEC or equivalent and Sangamo.

The Principal Investigator should maintain a list of appropriately qualified persons who are delegated to perform significant study-related studies. In addition, the Principal Investigator should maintain a signature sheet to document signatures and initials of all persons authorized to make entries and/or corrections on the source documents and electronic CRFs.

### **15.2 Record Retention**

The Principal Investigator shall retain records required to be maintained under this part for a period of 2 years following the date a marketing application is approved for the drug for the indication for which it is being investigated. If no application is to be filed or if the application is not approved for such indication, the Principal Investigator shall retain these records until 2 years after the investigation is discontinued and the appropriate regulatory authority (e.g., FDA/MHRA or equivalent) is notified. Study records shall be kept for at least 25 years or the maximum period by applicable policy or regulation (whichever is greater). However, these documents should be retained for a longer period if required by the applicable regulatory requirements or by an agreement with Sangamo. It is the responsibility of Sangamo to inform the Principal Investigator as to when these documents no longer need to be retained.

### **15.3 Case Report Forms**

The Principal Investigator is responsible for the quality of the data recorded on the CRF. The data recorded should be a complete and accurate account of the subject's record collected during the study.

Clinical data will be recorded on CRFs provided by Sangamo. All forms must be legible and complete. The Principal Investigator must review all entries for completeness and correctness. When changes or corrections are made on any CRF, an audit trail will be generated to record date and time when a change is made, who made the change, and reason for the change as needed. The original entry should not be obscured.

The Principal Investigator agrees to complete and sign CRFs in a timely fashion at the end of the study, and to make them available to the Study Monitor for full inspection. In addition, all data queries should be resolved promptly.

#### **15.4 Termination of the Study**

Sangamo retains the right to terminate the study and remove all the study materials from the study site at any time and for any reason. Specific instances that may precipitate such termination are as follows:

- Completion of the study at an investigational site
- Principal Investigator withdrawal from participation in study
- Termination of study by Sangamo

#### **15.5 Study Monitoring**

Sangamo, as Sponsor of this study, is responsible to regulatory authorities for ensuring the proper conduct of the study with regard to protocol adherence and validity of the data recorded on the CRFs presented to the regulatory authorities. Sangamo has therefore assigned a Clinical Monitor and a Medical Monitor to this study. Their duties are to aid the Principal Investigator and, at the same time, Sangamo in the maintenance of complete, legible, well-organized, and easily retrievable data. In addition, a Sangamo Study Monitor will ensure an understanding of the protocol, reporting responsibilities, and the validity of the data.

Individual study sites will be monitored by a Sangamo representative at appropriate intervals to assure satisfactory consenting process, data recording, and protocol adherence. To perform their roles well, the Sangamo monitors must be given direct access to primary subject data (source documents) that support data entered onto the CRFs. The Principal Investigator and staff are expected to cooperate and provide all relevant study documentation in detail at each site visit on request for review. Each study center will also be routinely monitored by telephone and/or by email to keep abreast of subject status and to answer questions.

Regulatory authorities, the IRB/IEC or equivalent, and/or Sangamo's Clinical Quality Assurance group may request access to all source documents, CRFs, and other study documentation for on-site audit or inspection. Direct access to these documents must be guaranteed by the Principal Investigator, who must provide support at all times for these activities.

The Principal Investigator or designated person should agree, as a minimum requirement, to record the following information in the subject notes:

- Protocol identification number, brief description, or title of study.
- Date and statement that subject has given written informed consent.
- All study follow-up visit dates.
- AE as described in [Section 10](#) of this protocol.

Entries in the subject notes must contain the signature or initials of the person making the entries.

The Study Monitor will perform source data verification at each monitoring visit.

#### **15.6 Confidential Information and Publication**

All information provided by Sangamo to the Principal Investigator and any data or results generated in the performance of this clinical trial are considered confidential and remain the sole property of Sangamo. The Principal Investigator shall maintain this information in confidence and

use this information solely for in the conduct of the study unless otherwise expressly agreed to in writing by Sangamo.

The Principal Investigator understands and agrees that Sangamo shall have the right to use the data or results generated in the performance of the study for any purpose, including in registration documents for regulatory authorities in the U.S. or abroad, or for public dissemination in the form of papers, abstracts, posters, or other informational materials to be presented at scientific meetings, or published in professional journals, or as a part of an academic thesis. The Principal Investigator further understands and agrees that Sangamo shall have the right to first publication of the data or results of the study, which is intended to be a joint, multi-center publication of the study results made by Sangamo in conjunction with the Principal Investigators from all appropriate investigational sites contributing data, analysis, and comments. Authorship of publications resulting from this study will be based on customary standards for attribution of authorship taking into consideration factors such as significance of contribution to the design of the study, analysis and interpretation of the data, and critical review of the publication. Subsequent to the first publication of the study results by Sangamo, the Principal Investigator may publish the Principal Investigator's site specific data or results. If the Principal Investigator wishes to publish the Principal Investigator's site specific data or results, a copy of such proposed publications, papers, abstracts, or other written materials, or an outline of any proposed oral presentations, shall be submitted to Sangamo for review at least 60 days prior to submission of such written materials for publication, or any proposed oral presentation. Sangamo shall have the right to review and comment on such written material or outline, and to confirm the accuracy of the data described therein by comparison with that collected during the course of this study. In addition, Sangamo shall have the right to require the Principal Investigator to, and Principal Investigator shall, remove specifically identified confidential information of Sangamo (other than the data or results of the study) and/or delay the proposed publication for an additional 60 days to enable Sangamo to file patent applications.

### **15.7 Study Funding**

The costs necessary to perform the study will be agreed to by the Principal Investigator and/or the management of the study facility, and will be documented in a separate financial agreement. All financial agreements will be signed by the Principal Investigator and Sangamo.

## APPENDIX 1: SCHEDULE OF EVENTS

PROCEDURE	Screening (q) (within 3 months of Baseline)	Baseline (within 21 days prior to SB-318 infusion)	Hospital or Acute Care Facility		Day (+/-1 day)	Week (+/-1 week)												Month (+/-1 month)							ETV		
			Day 0	Day 1		2	4	6	8	12	16	20	24	28*	32*	36	40*	44*	48	52*	15	18	21	24	27	30	33
Informed Consent	X																										
Medical History	X																										
Concomitant Medications	X	X	X	X		X	X	X	X	X	X	X	X	X	X	X	X	X	X	X	X	X	X	X	X		
Inclusion/Exclusion	X																										
Demographics	X																										
Physical Examination	X	X	X	X		X	X	X	X	X	X	X	X	X	X	X	X	X	X	X	X	X	X	X	X		
Vital Signs (a)	X	X	X	X		X	X	X	X	X	X	X	X	X	X	X	X	X	X	X	X	X	X	X	X		
AE Assessment	X	X	X	X		X	X	X	X	X	X	X	X	X	X	X	X	X	X	X	X	X	X	X	X		
ERT Administration Log	X	X	X			X	X	X	X	X	X	X	X	X	X	X	X	X	X	X	X	X	X	X	X		
JROM (b)		X																				X	X	X	X	X	
Neurologic Cranial Nerve Exam and Muscle Strength Testing of Upper Extremities (b)		X																				X	X	X	X	X	
12-Lead ECG	X	X																				X	X	X	X	X	
ECHO	X																					X					
Chest X-ray	X																										
Pregnancy Test (c)	X	X	X																								
Clinical Laboratory Tests	X	X		X			X	X	X	X	X	X	X	X	X	X	X	X	X	X	X	X	X	X	X		
Liver Panel (d)	X	X																				X	X	X	X	X	
MPS I Gene Sequencing (f)	X																										
SNP Analysis (f)	X																										
Viral Load	X																										
Neutralizing Antibodies to AAV2/6	X																										
Chimerism Assay (g)		X																				X					X
GAG Testing in Urine	X (h)	X																				X	X	X	X	X	X
IDUA/GAG Testing in Blood (i)	X	X																				X	X	X	X	X	X
Circulating AFP	X																					X	X	X	X	X	X
Vector Genome PCR in Plasma																											
Vector Genome PCR in Plasma, Saliva, Urine, Stool, and Semen (i)		X																				X	X	X	X	X	X
PFTs (b)	X	X																				X	X	X	X	X	X

PROCEDURE	Screening (q) (w/in 3 months of Baseline)	Baseline (w/in 21 days prior to SB-318 infusion)	Hospital or Acute Care Facility	Day 7 Day 0 (+/-1 day)	Week												Month						EIV			
					2	4	6	8	12	16	20	24	28*	32*	36	40*	44*	48	52*	15	18	21	24	27	30	33
6MWT (b)		X											X					X			X	X	X	X	X	X
Visual Acuity Test & Corneal Cludging Exam		X											X					X			X				X	X
VABS-II	X	X											X					X			X	X	X	X	X	X
Neurocognitive Abilities Assessment	X																									
Neurocognitive Abilities Testing (k)		X											X					X			X	X	X	X	X	X
MRI of Liver	X												X					X			X	X	X	X	X	X
MRI of Brain and Cervical Spine (l)		X																X					X			X
ACTH Stimulation (Cosyntropin) Test (m)		X (prior to prednisone)											X													
Liver Biopsy (n)		X											X					X								
Lumbar Puncture (n)		X												X					X							
Immunogenicity Assays (o)		X							X	X			X			X		X			X	X				
Prednisone (or equivalent corticosteroid) Administration (p)		X	X						X																	
SB-318 Infusion			X																							

\* Week 28, 32, 40, 44, and 52 study visits have assessments that do not require evaluation at the clinical site, and therefore may be conducted remotely. Blood and urine samples at these visits may be collected by a qualified home health nurse. For these study visits, GAG testing in urine may be waived for subjects who do not reside in the U.S. Assessments for AEs, concomitant medications and ERT administration log may be conducted remotely over the phone by study staff.

§ Study subjects may participate in the LTFU Study after 12 months of follow-up in this study, in which case an EOS visit may be conducted any time after Week 52 but before the next scheduled study visit. Study participants who wish to enroll in the LTFU Study with less than 12 months of follow-up in this primary study may be considered on a case-by-case basis at the judgement of the Principal Investigator and after consultation with the Sponsor. In these cases, the EOS visit may be conducted at any time on this study.

- Vital signs (height, weight, systolic/diastolic blood pressure, heart rate, respiratory rate, and temperature; for frequency, refer to the Study Reference Manual.
- As permitted by subject's capacity.
- Serum pregnancy test will be performed at Screening and Baseline visits. Urine pregnancy test will be performed on the Day 0 visit if >7 days from Baseline pregnancy test. Urine pregnancy tests will be performed until Week 48 or until 3 consecutive plasma samples are negative for AAV2/6, whichever occurs first.
- Liver panel does not need to be drawn as a separate sample if samples for Clinical Laboratory Tests are obtained at the same visit.

- e. Liver panel will be performed twice a week for the first 20 weeks post-SB-318 infusion and may be remotely. Blood samples will be drawn 2-4 days apart when possible, except for the first week when it will be drawn on the Day 1 and Day 7 visits. Liver function tests will subsequently be conducted at all indicated study visits.
- f. For adult subjects (cohorts 1 through 3), the assay will be performed on blood or saliva samples. For post-transplant subjects, the assay will be performed on saliva samples only. For pediatric subjects (cohorts 4 through 7), saliva samples are preferred.
- g. For post-HSCT patients only.
- h. During Screening, samples for GAG testing in urine will be collected on 3 separate days, each collection occurring at least 7 days after the previous. All samples for GAG testing in the urine must be collected at least 7 days after ERT administration [+/- 1 day] but prior to the next ERT infusion.
- i. For IDUA/GAG testing in blood, samples must be obtained 7 days after ERT administration (+/- 1 day) and prior to the next ERT infusion. GAG and IDUA levels in blood will both be measured concurrently from the same blood sample.
- j. Each type of sample (plasma, saliva, urine, stool, semen) will be collected until 3 consecutive specimens of that sample type are reported as negative or undetectable for vector genome. Collection of semen samples may be waived for male pediatric subjects (cohorts 4 through 7) at the discretion of Principal Investigator.
- k. As permitted by subject's capacity. Neurocognitive abilities testing in pediatric subjects will be done by VABS-II and by WASI-II, WPPSI-IV, or BSID-III, as appropriate based on the Neurocognitive Abilities Assessment performed at Screening.
- l. Baseline MRI of brain and cervical spine may be obtained at Screening (together with MRI for liver) instead of at Baseline at the discretion of the Principal Investigator.
- m. Should prednisone or equivalent corticosteroid treatment be continued or repeated due to increased transaminase activity, the ACTH stimulation test will be repeated at the end of taper. Vital signs should be monitored and recorded every hour during the ACTH stimulation test.
- n. Unless contraindicated by a Principal Investigator or physician.
- o. May be waived for pediatric subjects (cohorts 4 through 7) at the discretion of the Principal Investigator to minimize required blood volumes.
- p. See [Appendix 3](#).
- q. For subjects who are re-screening for participation in the study, assessments including ECHO, chest X-Ray, PFTs, and MRI of liver and/or brain and cervical spine performed for the Screening of a subject in the previous 6 months may be used for evaluation of inclusion/exclusion criteria at the judgement of the Principal Investigator. Further, genetic marker analysis including SNP analysis and MPS I sequencing will not be repeated as results of these assessments do not change over time.

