#### **6.8 Weeks 12, 16, 20, 24, 28, 32, 36, 40, 44, 48, and 52 (+/- 1 week)**

The following assessments and procedures will be performed unless otherwise stipulated:

- Review and record concomitant medications.
- Physical examination (at Weeks 12, 16, 20, 24, 36, and 48 only).
- Vital signs (at Weeks 12, 16, 20, 24, 36, and 48 only).
- Assessment of AEs.
- ERT administration log.
- JROM (at Weeks 24 and 48 only).
- Neurologic cranial nerve exam and muscle strength testing of the upper extremities (at Weeks 24 and 48 only).
- 12-lead ECG (at Weeks 24 and 48 only).
- ECHO (at Week 48 only).
- Pregnancy test (females of childbearing potential only; at Weeks 12, 16, 20, 24, 36, and 48 only).
- Clinical laboratory tests (at Weeks 12, 16, 20, 24, 36, and 48 only).
- Liver panel (twice weekly until Week 20; then at Weeks 24, 28, 32, 36, 40, 44, 48, and 52; may be conducted remotely until Week 20 and at Weeks 28, 32, 40, 44, and 52).
- Chimerism assay (at Weeks 12 and 48 only; for post-HSCT subjects only)
- GAG testing in urine.
- IDUA / GAG testing in blood (at Weeks 12, 16, 20, 24, 36, and 48 only).
- Circulating AFP level (at Weeks 12, 24, and 48 only).

- Vector genome PCR in plasma, saliva, urine, stool, and semen (males only) (at Weeks 12, 16, 20, 24, 36, and 48 only).
- PFTs (at Weeks 24 and 48 only).
- 6MWT (at Weeks 24 and 48 only).
- Visual acuity test and corneal clouding exam (at Weeks 24 and 48 only).
- Neurocognitive abilities tests by WASI-II, WPPSI-IV, or BSID-III, and by VABS-II (at Weeks 24 and 48 only).
- MRI of liver (at Weeks 24 and 48 only).
- MRI of brain and cervical spine (at Week 48 only).
- ACTH stimulation (cosyntropin) test (at Week 20 only or at end of prednisone or equivalent corticosteroid taper; see [Appendix 3](#)).
- Liver biopsy (at Weeks 24 and 48 only).
- Lumbar puncture (at Weeks 24 and 48 only).
- Immunogenicity assays (at Weeks 12, 24, 36, and 48 only).
- Prednisone or equivalent corticosteroid administration (through Week 20 only).

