#### 9.11 Pregnancy Testing and Contraception Requirements

Pregnancy testing will be conducted on all female subjects of childbearing potential (for details, refer to the Laboratory Manual).

A female subject is considered of childbearing potential (i.e., fertile) following menarche and until becoming post-menopausal unless permanently sterile. A postmenopausal state is defined as no menses for 12 months without an alternative medical cause. Permanent sterilization methods include hysterectomy, bilateral salpingectomy, and bilateral oophorectomy.

Female subjects of childbearing potential with a positive pregnancy test at Screening will not be enrolled in the study.

Female subjects of childbearing potential will have a serum pregnancy test at the Screening and Baseline visits. A urine pregnancy test will be performed at Day 0 if >7 days from Baseline pregnancy testing. Subsequently, urine pregnancy tests will be done at the indicated visits (see [Section 6](#) and [Appendix 1](#)) until at least 3 consecutive plasma samples after administration of SB-318 are negative for AAV2/6. Additional pregnancy tests will be performed at any visit at which pregnancy status is in question. A serum pregnancy test will be performed in the event of a positive or equivocal urine pregnancy test result, or can be performed if pregnancy test by urine is not feasible at the discretion of the Principal Investigator.

Pregnancy in a subject or a subject's partner must be reported to the Sponsor (see [Section 10.7](#)).

Both male and female sexually mature subjects must agree to use a barrier contraceptive method for prevention of AAV transfer as follows: for female subjects this means that the subjects' partners must use a condom from the time of dosing with SB-318 until at least 3 consecutive plasma samples after administration of SB-318 are negative for AAV2/6; for male subjects this means that the subjects must use a condom and must refrain from sperm donation from the time of SB-318 administration until at least 3 consecutive semen samples after administration of SB-318 are negative for AAV2/6.

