Additionally, female participants of child-bearing potential who have not undergone a total hysterectomy or bilateral salpingo-oophorectomy and who are sexually active must consent to use a highly effective method of contraception from the time of dosing with SB-318 until at least 3 consecutive plasma samples after administration of SB-318 are negative for AAV2/6. Examples of highly effective methods of contraception include:

- Combined (estrogen and progestogen containing) hormonal contraception associated with inhibition of ovulation (e.g., oral, intravaginal, transdermal).
- Progestogen-only hormonal contraception associated with inhibition of ovulation (e.g. oral, injectable, implantable).
- Intrauterine device or intrauterine hormone-releasing system.

- Bilateral tubal occlusion.
- Male partner sterilization (i.e., vasectomy).
- Sexual abstinence (i.e., refraining from heterosexual intercourse during the entire period of risk associated with SB-318, when this is in line with the preferred and usual lifestyle of the subject).

For details, refer to the Laboratory Manual.

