## **9.21 Vector Genome PCR**

Plasma, saliva, stool, and semen (males only) samples will be analyzed by PCR to determine clearance of SB-318 vector genomes. Each type of sample (plasma, saliva, urine, stool, semen) should be collected until 3 consecutive specimens of that sample type are reported as negative or undetectable for vector genome. Collection of semen samples may be waived for pediatric subjects (cohorts 4 through 7) at the discretion of the Principal Investigator. For details, refer to the Laboratory Manual.

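### The Week 48 cap on routine urine pregnancy tests acts only on women not yet cleared of vector, contradicts Section 9.11, and Section 6 lists no later visit for the PCR still owed

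*Protocol*

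**What the plan says.** **Pregnancy tests.** Appendix 1, footnote c, reads: "Urine pregnancy tests will be performed until Week 48 or until 3 consecutive plasma samples are negative for AAV2/6, whichever occurs first". SAP 9.3 carries the same rule. Section 9.11 ties the tests to the indicated visits and names only clearance as their end point: "until at least 3 consecutive plasma samples after administration of SB-318 are negative for AAV2/6. Additional pregnancy tests will be performed at any visit". The additional tests mentioned there are for cause, when a pregnancy is suspected. Section 9.11 gives no week limit. The last visit in Section 6 with a routine test is Week 48: "Pregnancy test (females of childbearing potential only; at Weeks 12, 16, 20, 24, 36, and 48 only".

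**Contraception.** Section 9.11 asks sexually active women of childbearing potential for a "highly effective method of contraception from the time of dosing with SB-318 until at least 3 consecutive plasma samples" are negative. Partners' condom use has the same end point. Men must use condoms and "must refrain from sperm donation from the time of SB-318 administration until at least 3 consecutive semen samples" are negative. None of these duties has a week limit.

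**Vector PCR.** Section 9.21 says: "Each type of sample (plasma, saliva, urine, stool, semen) should be collected until 3 consecutive specimens of that sample type are reported as negative". An undetectable result also counts. Appendix 1, footnote j, says the same. Section 6.8 lists "Vector genome PCR in plasma, saliva, urine, stool, and semen (males only) (at Weeks 12, 16, 20, 24, 36, and 48 only".

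**After Week 48.** Section 6.8 lists neither test at Week 52. Section 6.9 (Months 15 to 36), Section 6.10 (early termination) and Sections 6.11 to 6.13 (ERT withdrawal) list neither at all. SAP 8.2.4 and the shell for Table 14.2.3 also end vector clearance at Week 48.

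**The concern.** A woman who has had three consecutive negative plasma samples has already stopped routine testing under either rule, so the Week 48 cap changes nothing for her. It changes something only for a woman who reaches Week 48 uncleared, whom Section 9.11 still regards as needing contraception because of the vector. The cap thus withdraws routine pregnancy detection from the only group in whom the risk period is still open.

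A linked gap concerns the sample that closes that period. The protocol requires PCR to continue until three consecutive negatives, but staff working from the visit lists in Section 6 find no PCR after Week 48. If it is overlooked, the contraception duty stays open because the evidence to end it was not collected. The same applies to semen PCR and the restrictions on men. At stake are routine detection of an early pregnancy, an avoidably long restriction on the subject, and a clearance summary (a secondary endpoint) that stops before late clearers clear.

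**Working it through.** No sample size, power or error rate is involved. The check is a count over the visit lists.

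**Inputs.**
- Post-dose plasma PCR (Sections 6.5 to 6.8): Day 1, Day 7, Weeks 2, 4, 8, 12, 16, 20, 24, 36, 48, which is 11 samples. Semen has no Day 1 sample, so 10.
- Post-dose urine pregnancy tests (Sections 6.7 and 6.8), leaving aside the conditional Day 0 test: Weeks 4, 8, 12, 16, 20, 24, 36, 48, which is 8 tests.
- Visits after Week 48: Week 52 and Months 15, 18, 21, 24, 27, 30, 33, 36, which is 1 + 8 = 9.
- Clearance: three consecutive negatives of the sample type.

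**Step 1: when can clearance be shown?** For a subject not already cleared, count the samples after the last positive and find the third. The last two columns add sampling at later visits. All columns assume no missed sample and no new positive.

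| Last positive | Listed samples left | Third negative, as listed | If sampling continues from Week 52 | If it resumes at Month 15 |
|---|---|---|---|---|
| Week 16 | 4 | Week 36 | – | – |
| Week 20 | 3 | Week 48 | – | – |
| Week 24 | 2 | cannot be shown | Week 52 | Month 15 |
| Week 36 | 1 | cannot be shown | Month 15 | Month 18 |
| Week 48 | 0 | cannot be shown | Month 18 | Month 21 |

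A last positive at Week 20 uses every remaining listed sample, so one missed draw also leaves that subject uncleared. The table holds for semen too, because the two lists differ only at Day 1.

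**Step 2: how long is the gap?** Week 48 is 48 × 7 = 336 days, and 336 / 30.4375 = 11.04 months. To Month 36 this leaves 36 − 11.04 = 24.96, about 25 months and 9 visits without a routine pregnancy test. A subject may instead move to the long-term follow-up study between Week 52 and Month 15. Month 15 is 15 × 30.4375 = 456.6 days, so the gap within this study is then between 52 − 48 = 4 weeks and (456.6 − 336) / 7 = 17.2 weeks.

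**Step 3: how many subjects?** The documents give no figure for vector persistence in plasma or semen. The study maximum is 27, and the base plan is 1 + 2 × 6 = 13, but these totals count everyone, including children aged 5 to 11 and subjects who clear early. They are not estimates of the number affected.

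**Step 4: the texts side by side.** Footnote c and SAP 9.3 give two stopping conditions and take the earlier. Section 9.11 gives one, clearance, for tests and contraception alike. They agree for anyone cleared by Week 48 and differ only for those who are not. Even on Section 9.11 alone, tests fall at the indicated visits, and Section 6 indicates none after Week 48. The Appendix 1 grid is misaligned in the extracted text and could not be read, so the visit counts rest on Section 6.

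**The case against.** The case for leaving the text alone is fair in several respects.

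- **The body of the protocol does not cap testing.** Section 9.11 runs tests to clearance, so footnote c can be seen as a wording mismatch. That stands, but the footnote is the schedule's own rule and the SAP repeats it, so a site can follow either.
- **The PCR duty already exists.** A reader might infer that vector sampling ends at Week 48. It does not: Section 9.21 and footnote j, the latter within the schedule itself, require it until three negatives. The Laboratory Manual, not available here, may say how late samples are arranged. What remains is that Section 6 names no later visit for them.
- **The end of contraception is defined.** A reader might infer that the restrictions have no end. They end on an event, the third negative sample, and were never tied to a visit.
- **Late PCR results are not lost.** SAP Section 4 puts all collected data in listings, and Listing 16.2.9.6.1 has no visit limit. They would be missing only from the Table 14.2.3 summary.
- **Safeguards remain.** Section 9.11 provides a test whenever pregnancy is in question, and Section 10.7 requires reporting. There is one infusion and no later dose to withhold, steroids are scheduled to stop by Week 20, and the last routine liver biopsy and lumbar puncture are at Week 48. A reader might infer that uncleared women go unmonitored for pregnancy; only routine detection is lost.

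These points reduce the size of the concern. None supplies a routine pregnancy test, or a listed PCR visit, after Week 48.

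**Conclusion.** The concern holds as a minor safety alignment. Footnote c and SAP 9.3 conflict with Section 9.11, and the cap takes effect only in women whom the protocol still treats as within the vector risk period. On the Section 6 lists, an uncleared subject positive at Week 24, 36 or 48 cannot show clearance. For such a woman, the time without routine tests is about 25 months over 9 visits if she stays to Month 36, or 4 to about 17 weeks in this study if she transfers after Week 52.

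The 25 months is a worst case for an individual and says nothing about frequency. A reader might take the enrolment maximum of 27 as the number exposed, but the documents do not support that: only uncleared women of childbearing potential lose routine pregnancy tests, and that group may be empty.

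The conclusion assumes that the Appendix 1 grid matches Section 6, and that the Laboratory Manual does not already schedule late sampling. The testing rules of the long-term follow-up study are not in these documents.

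**What to change.** 1. Delete the Week 48 limit from Appendix 1, footnote c, and from SAP 9.3, so that both match Section 9.11.
2. In Sections 6.8 to 6.10 and Appendix 1, add two conditional items at Week 52, Months 15 to 36/EOS and early termination:
   - a urine pregnancy test for women of childbearing potential, until three consecutive plasma samples are negative;
   - vector genome PCR for any sample type (plasma, saliva, urine, stool, semen) not yet negative on three consecutive specimens.
3. Keep the pediatric semen waiver, and let semen wait until Month 15 if Week 52 is done remotely.
4. Extend SAP 8.2.4 and the Table 14.2.3 visit list to these visits.

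**Cost.** Protocol and SAP wording, plus one urine test and PCR samples already required by Section 9.21, at existing visits and for uncleared subjects only. With sampling from Week 52, the minimum is 1, 2 or 3 extra sampling visits for a last positive at Week 24, 36 or 48, and the maximum is 9. Appendix 1 already lets a home nurse take blood and urine at Week 52. Pregnancy results are only listed, so that part adds no analysis; the clearance table gains visits. Subjects already cleared see no change.
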